## **Procedures & Interventions**

**Screening (30 minutes).** Initial eligibility will be determined via telephone with a Screening Questionnaire. Individuals who do not meet criteria for the study will be referred to community drinking reduction programs. The phone screening form will be destroyed for those who are not eligible. First and last names of those who are excluded will be maintained to prevent re-screening. De-identified demographic information and reasons for ineligibility for those who are ineligible will be recorded in a separate document without identifiers for reporting purposes. Eligible individuals will be scheduled for a baseline assessment session. Phone screening forms and contact information for participants who are screened in will be maintained in a password protected file. The phone screening form will be de-identified and only linked to the participant with the participant ID.

**Baseline (up to 5 hours).** Informed consent will be obtained, and participants will complete the Handedness Questionnaire and pregnancy test (fertile female participants only). Participants will complete assessments listed in Table 1. Participants will also complete a baseline tDCS stimulation session lasting less than 10 minutes. This baseline session will be to familiarize the participants to tDCS outside of the group setting, to explain the stimulation protocol, and to answer any questions that participants might have about the tDCS procedure. Participants in the active condition who have difficulty tolerating the 2.0 mA current during the baseline stimulation session will be tested at 1.5 mA. If 1.5 mA is tolerated then participants will be enrolled in the trial at 1.5 mA. If 1.5 mA is not tolerated during the baseline stimulation session then participants will be deemed ineligible. Participants who fail study eligibility requirements at this point will be compensated for their time and referred to community alcohol treatment programs.

**MBRP + tDCS Sessions (2 hour treatment groups + 30 minutes for initial assessments, breathalyzer, pregnancy tests, and withdrawal assessments).** Following the baseline session, participants will begin a series of weekly or twice weekly group MBRP + tDCS intervention sessions for up to eight weeks at the PCNC. To maximize the availability of groups and to accommodate various therapist schedules we will run groups either twice per week for four weeks or once per week for eight weeks. All participants will receive up to 8 two hour sessions of MBRP + tDCS, regardless of the group schedule.

At the beginning of each session the subject will be asked to complete a baseline mood assessment, all participants will be breathalyzed, and fertile female participants will be asked to complete a pregnancy test. Women who are pregnant will not be allowed to complete the study and will be told in private of their pregnancy status. Participants who have a BAC > 0.0 will be rescheduled, given snacks and water until their BAC is reduced to < 0.04 in accordance with NIAAA guidelines, and will be provided a taxi voucher. We will also assess all participants for potential alcohol withdrawal at the time of each tDCS session. If participants show significant signs of withdrawal and/or have a score of 8 or greater on the Clinical Institute Withdrawal of Alcohol Assessment Scale (CIWA), then the research assistant will recommend the subject go to the UNM Hospital for further assessment. Our previous studies with more severely dependent individuals occasionally encountered patients with severe withdrawal, and this protocol was used successfully without any adverse consequences. Subjects with CIWA scores of 8 or greater at any session will be excluded from the research study. These aspects of the study will take approximately 30 minutes to complete.

Subjects will then receive 30 minutes of either active or sham tDCS stimulation, depending on their group assignment. A sensation questionnaire will be administered after 5 minutes of tDCS, 15 minutes, and 25 minutes of tDCS. At the end of tDCS stimulation participants will be asked a few questions regarding their mood and mental state to make sure that they have no lingering effects of the stimulation. After tDCS stimulation the remaining time will be used for MBRP session content (described below).

**Post-Treatment Assessment (up to 5 hours).** After completing the MBRP + tDCS sessions (i.e., up to two weeks after final tDCS/mindfulness session), participants will complete the assessments listed in Table 1 at the PCNC.

**Follow-Up Assessment (up to 2 hours).** At 2 months following completion of MBRP+tDCS, participants will complete the assessments listed in Table 1, with the exception of EEG, at the PCNC.

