### I. *Target Population and Inclusion/Exclusion Criteria*

Participants for the proposed research include up to 350 individuals ages 18 and over who will be recruited from the Albuquerque Metropolitan Area using the following inclusion criteria:

- 1) interested in reducing alcohol drinking and consumed alcohol in past 30 days
- 2) right-handed
- 3) able to communicate in English

The inclusion criteria are based on our long-term goal of developing an intervention with broad appeal for most individuals who are interested in reducing drinking. The right-handed inclusion is based on the fact that the majority of people are right-handed and the effects of tDCS may be influenced by handedness (a proxy for hemispheric dominance; Schade et al., 2012). Ultimately we plan to develop separate tDCS montages that are specific to right and left hemisphere dominance, but for the purposes of this initial study we opted for increasing internal validity by excluding left-handed individuals.

The following exclusion criteria will be used for all participants

- (1) lifetime diagnosis of schizophrenia or bipolar disorder or current SUD other than nicotine or marijuana assessed via the phone screening questionnaire
- (2) cardiac pacemaker
- (3) implantable defibrillator
- (4) metal objects in upper body that might interfere with tDCS, or that tDCS may interfere with their function, including metal plates, screws and prosthetics in head, certain older tattoos and permanent makeup using metal containing inks, aneurysm clips, neural stimulators of any kind, ear implants or hearing aids, insulin pumps, drug infusion devices and dental appliances
- (5) for females, pregnant or attempting to get pregnant
- (6) history of seizures or seizure disorder
- (7) allergic to latex, rubber, conductive medium like saline or electrode gel
- (8) if assigned to active tDCS and unable to tolerate 1.5 mA of tDCS during a baseline stimulation session
- (9) history of severe alcohol withdrawal including tremors, seizures, or delirium tremens
- (10) currently or previously prescribed anti-seizure medications or medications for alcohol withdrawal
- (11) score of 8 or greater on the Clinical Institute Withdrawal of Alcohol Assessment Scale – Revised at any tDCS sessions
- (12) unable to attend treatment groups at scheduled time and unwilling to wait for group treatment at a time that works for the participant

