Clinical Institute Withdrawal Assessment of Alcohol Scale, Revised	Measure of current alcohol withdrawal symptoms	X		
Blinding Questionnaire	One question assessing knowledge of condition		X	

**Primary Drinking Outcome.** The *Form 90* (Miller, 1996) is a semi-structured interview that gathers daily calendar-based alcohol and illicit drug use data. A 2-month assessment window will be used at each of the time-points. The *Form 90* will be used to derive estimates of the primary outcome: drinks per drinking day. The *Form 90* has demonstrated reliability in the collection of alcohol and drug use data (Maisto, Conigliaro, Gordon, McGinnis, & Justice, 2008; Sobell, Brown, Leo, & Sobell, 1996).

**Weekly During Treatment Measures.** An abbreviated assessment battery will be administered weekly during treatment to assess state mindfulness (Toronto Mindfulness Scale (Lau et al., 2006)), mindfulness practice in the prior week, craving (PACS; Flannery Volpicelli, & Pettinati, 1999), negative urgency and lack of planning items from the UPPS (Littlefield et al., 2015; Whiteside & Lynam, 2001), and negative affect (Short Forms of Anger, Sadness, Stress from NIH Emotions Toolbox; Salsman et al., 2013).

**Behavioral Tasks.** All behavioral tasks will be completed via computer during EEG to provide a measure of electrical brain activity during rest and completion of the tasks. To examine inhibitory control, we will use a *Stop Signal Task* (Logan, Van Zandt, Verbruggen, & Wagenmakers, 2014) in which participants make left-right judgments of the directionality of an arrow presented on the screen. For each trial, a circle will appear for 500 ms, followed by a left or right-pointing arrow for up to 1 second, and between 500 ms and 2500 ms jittered inter-trial interval to reduce anticipatory responses. Approximately 25% of trials will be "stop trials" with a tone played to signal participants to inhibit the

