## II. *Data Analysis/Statistical Considerations*

**Power analysis and sample size considerations.** We conducted power analyses using effect sizes from a pilot study ( $d=0.64$  and  $d=0.43$  on drinks per drinking day at post- and 2-month follow-up). With desired power  $>0.80$ , a two-tailed  $\alpha < 0.05$ , and three time-points, we will need 70 participants to detect a medium effect of active tDCS + MBRP vs. sham tDCS + MBRP on drinks per drinking day at follow-up. For mediation analyses we will need 74 participants to detect a medium effect. Attrition of 15% is anticipated based on our pilot tDCS study and thus we propose to recruit  $n=86$  participants to allow for some attrition. We anticipate screening up to 350 participants in order to recruit a sample of 86 participants.

**Data Analyses and Missing Data.** The primary study aim is to test the overall efficacy of the active tDCS + MBRP intervention compared to a sham tDCS + MBRP group. We will use maximum likelihood estimation for all analyses, which provides the variance-covariance matrix for all available data and is the preferred method for estimation when some data are missing. Variables associated with missing data and those used in randomization (gender, age, treatment history) will be covaried in all analyses.

**Aim #1: Efficacy Analyses.** All assessment data will be analyzed for outliers and missing cases to detect any bias that might result from differential attrition. The efficacy of active tDCS + MBRP versus sham tDCS + MBRP will be examined using a generalized linear mixed model with drinks per drinking day at the end of treatment and follow-up as the primary outcomes. We hypothesize active tDCS will be associated with significantly larger reductions in drinks per drinking day following treatment, as compared to sham tDCS. Interim analyses to compare sham versus active tDCS treatment efficacy will be conducted in February 2017, after a sufficient number of subjects have been treated, and at the time of submitting our annual progress report to NIH, which will occur in June 2017.

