## III. *Participant Withdrawal*

If a participant wishes to withdraw from the study all of their information held at the Psychology Clinical Neuroscience Center will be destroyed. They have the right to withdraw their consent or stop participating at any time. They can refuse to answer any question(s) or refuse to participate in any procedure for any reason. Refusing to participate in this study will not result in any penalty or loss of benefits to which they are otherwise entitled.

If they wish to stop participating at any time, they can notify a study team member or [name] at [contact], Monday through Friday, 9am - 5 pm. Alternatively, they can write to her at the PCNC, [name]. All of this information is given to them upon their admittance to the study in their consent form. On the other hand, if the experimenters

decide that a participant is not eligible to continue with the study, their participation may be terminated without their consent.

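### Participants removed at a treatment session for a CIWA score of 8 or more, or for pregnancy, appear to lose all later drinking outcomes; the CIWA losses may be informative

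*Combined protocol and SAP*

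**What the plan says.** Exclusion criterion 11 (Study Design, section I) lists a "score of 8 or greater on the Clinical Institute Withdrawal of Alcohol Assessment Scale – Revised at any tDCS sessions". The session procedures (Procedures & Interventions, MBRP + tDCS Sessions) apply it in both arms: "We will also assess all participants for potential alcohol withdrawal at the time of each tDCS session". They give the consequence as "Subjects with CIWA scores of 8 or greater at any session will be excluded from the research study". The same paragraph sets the pregnancy rule: "Women who are pregnant will not be allowed to complete the study and will be told in private of their pregnancy status". Under III. Participant Withdrawal, if staff "decide that a participant is not eligible to continue with the study, their participation may be terminated without their consent".

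These rules act after assignment. The arm is already in force at the baseline stimulation session, before the first group session: "Participants in the active condition who have difficulty tolerating the 2.0 mA current during the baseline stimulation session will be tested at 1.5 mA".

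The primary outcome, drinks per drinking day, comes from the Form 90 at baseline, post-treatment and 2 months, and "A 2-month assessment window will be used at each of the time-points". The post-treatment assessment is scheduled once the MBRP + tDCS sessions are completed, and the follow-up 2 months after that completion. The weekly battery covers mindfulness, practice, craving, urgency and planning items, and negative affect. It has no drinking measure.

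On missing data, the statistical section says "We will use maximum likelihood estimation for all analyses, which provides the variance-covariance matrix for all available data". It adds variables associated with missingness as covariates and promises a check for bias from differential attrition. It does not mention these removals, and there is no intention-to-treat statement.

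**The concern.** A criterion listed under eligibility goes on operating through the treatment period, and its stated consequence is exclusion from the study, not only from stimulation. Form 90 is an interview and involves no stimulation, yet no assessment is clearly scheduled for someone who never completes the sessions. Staff following the text would reasonably stop collecting data.

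For the CIWA rule, the reason for the missing outcome is alcohol-related and arises after baseline, so those removed may differ from those retained in the quantity being compared. The arms would then no longer be compared as randomised. The stopping provision under Unanticipated Problems/Adverse Events, which turns on whether active participants drink more than sham, would rest on the same incomplete data.

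The pregnancy rule raises a lesser concern: randomised participants are lost to outcome follow-up without need, but nothing in the documents links that trigger to drinking.

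**Working it through.** **1. What a removed participant contributes.** Take someone in either arm who scores 8 or more at session 3. Criterion 11 and the session procedures exclude them from the study. The two later assessments are timed from a completion that does not happen. The weekly battery holds no drinking data. They contribute at most a baseline Form 90.

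**2. Can the planned analysis repair this?** Baseline covariates (gender, age, treatment history) need not carry the information in a trigger that arises later. The CIWA score and weekly craving and negative affect are observed, and the plan's wording would allow them as covariates. Two limits remain. Everyone at or above the threshold would lack later outcomes, so a model must extrapolate from those below it. Craving and negative affect are also hypothesised mediators (Hypothesis 2), so covarying them would adjust away part of the effect under test. The attrition check can show imbalance but cannot recover values.

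**3. The plan's own recruitment figure.** Starting from 74 (mediation) and 15% attrition: 74 × 1.15 = 85.1, or 86 rounded up to an even number. Dividing instead, 74 / 0.85 = 87.06, or 88. The stated 86 is reproduced by the first and is within 2 of the second. Expected with outcomes: 86 × 0.85 = 73.1.

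**4. How many might be removed.** No rate is given, so the per-session risk p is assumed. Removed over k sessions = 1 − (1 − p)^k.

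| p (assumed) | k = 8 | of 86 | k = 5 |
|---|---|---|---|
| 0.5% | 3.9% | 3.4 | 2.5% |
| 1% | 7.7% | 6.6 | 4.9% |
| 2% | 14.9% | 12.8 | 9.6% |

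The plan's whole attrition allowance is 0.15 × 86 = 12.9. Eight sessions is the maximum exposure; five is shown because the Background reports that only 50–60% attended most MBRP sessions in earlier trials.

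**5. If these losses come on top of the 15%** (assumed extra loss 2%, 5%, 10%):
- With outcomes: 86 × 0.83 = 71.4; 86 × 0.80 = 68.8; 86 × 0.75 = 64.5.
- Recruitment needed to keep 74: 74 / 0.83 = 89.2 (90); 74 / 0.80 = 92.5 (93); 74 / 0.75 = 98.7 (99).

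**6. Shift from an unequal split.** With 43 per arm, 4 removed in one arm and 1 in the other, and removed participants D drinks per drinking day away from the rest, the shift is (4/43 − 1/43) × D. For D = 2 to 5 this is 0.14 to 0.35 drinks. The split and D are assumed. With no SD in the plan, this cannot be set against the pilot effects.

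**7. Direction, if removal rises with drinking level.** Assumptions: a normal outcome with SD 1, the active arm lower by d, removal probability logistic in the outcome with slope 1 or 2 per SD, completers only, 2 million simulated per arm.

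| True d | Sham removed | Active removed (slope 1 / 2) | Completers' d (slope 1 / 2) |
|---|---|---|---|
| 0 | 2%, 5% or 10% | same as sham | 0.00 |
| 0.43 | 2% | 1.3% / 0.9% | 0.425 / 0.414 |
| 0.43 | 5% | 3.4% / 2.6% | 0.416 / 0.395 |
| 0.43 | 10% | 7.0% / 5.6% | 0.403 / 0.373 |
| 0.64 | 2% | 1.1% / 0.7% | 0.630 / 0.618 |
| 0.64 | 5% | 2.8% / 1.8% | 0.621 / 0.592 |
| 0.64 | 10% | 5.8% / 4.1% | 0.605 / 0.562 |

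Here sham loses more participants, the bias is toward no effect, and it is small when removals are rare.

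**The case against.** The strongest case against has four parts.

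- **Loss of Form 90 is inferred.** No sentence says that the interviews stop, and the withdrawal section says only that participation may be ended. This stands as a limit on wording: the loss is the plain reading, not a stated rule. It does not remove the point, because nothing says the interviews continue and both are timed from completing the sessions.
- **The events are probably rare.** Criteria 9 and 10 already exclude a history of severe withdrawal and withdrawal medication, CIWA is also scheduled at baseline, and the sponsor met severe withdrawal only occasionally in more dependent samples. The 15% attrition, taken from the pilot, may already include such removals. This stands.
- **The plan has some protection.** It uses all available data, allows covariates associated with missingness and checks for differential attrition. This is fair, but step 2 shows why it cannot be relied on here.
- **These are safety rules.** They are, and the point leaves them as they are. It concerns only whether outcomes are collected afterwards and how those participants are analysed.

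A reader might also infer that active tDCS, by speeding the reduction in drinking, would cause more withdrawal and so more removals in the active arm. The documents give no support for that mechanism; they link withdrawal only to more severe dependence. If removal rises with drinking level instead, step 7 shows the imbalance running the other way.

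**Conclusion.** The point holds in a limited form. As written, the CIWA and pregnancy rules remove randomised participants from the study during treatment in both arms and, read plainly, end their primary outcome data. The CIWA losses may be informative, and the planned analysis need not correct them. The pregnancy losses are avoidable but not outcome-related on anything in the documents, so it would be wrong to describe both rules as driven by drinking.

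The size is unknown. The 3 to 13 of 86 rests wholly on assumed rates, and the low end is more plausible. The direction is unknown too: attenuation is small under the one model worked through, and little or no bias is expected if tDCS affects neither drinking nor withdrawal. A claim that the trial is biased toward or against active tDCS would go beyond the documents. Severity is moderate: the likely effect is modest, but drinking data not collected at the time may be unrecoverable, and preventing the loss is cheap.

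**What to change.** Leave the stimulation, referral and stopping rules as the sponsor has them, and state what removal means for the data. In the session procedures and in the Post-Treatment and Follow-Up Assessment paragraphs, say that:

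- removal after assignment, for whatever reason the safety rules give, ends study treatment only;
- the post-treatment and 2-month Form 90 and questionnaires are still collected at the times at which they would have fallen due, by telephone if needed, from those who consent to continue;
- these participants are analysed in their assigned arm;
- removals are reported by arm and reason.

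Align criterion 11 and the Participant Withdrawal section with this wording, and add the assigned-arm statement to the statistical section.

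The cost is protocol wording and probably a few extra interviews. The trade-off is that the contrast will include some participants with incomplete treatment.

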**Secondary Aim: To examine mechanisms of drinking behavior changes following treatment.**

Hypothesis 2. Effect of active tDCS on drinks per drinking day at the 2-month follow-up will be mediated by greater mindfulness, greater inhibitory control and reductions in cue-reactivity, craving, and negative affect during treatment and at the post-treatment assessment. The effect of the “dose” of treatment, including session attendance and amount of mindfulness practice, on drinks per drinking day at 2-months will be mediated by greater mindfulness and inhibitory control and reductions in cue-reactivity, craving, and negative affect.

Hypothesis 3. Based on prior EEG studies of alcohol use disorder and mindfulness, we hypothesize significantly increased amplitude of the P3 (e.g., P300) component of the event-related brain potential (ERP) during cognitive inhibition and reduced P3 amplitude in response to alcohol cues in the active tDCS group at post-treatment, as compared to sham tDCS. Changes in ERPs among those who receive active tDCS with MBRP will be significantly associated with reductions in drinks per drinking day following treatment.

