**Secondary Aim: Mediation Analyses.** Mediation models will be estimated for weekly and post-treatment assessments of mindfulness, inhibitory control, cue reactivity and craving, and negative affect using the product of coefficients method. We will look at self-report and behavioral assessments of each proposed mediator in separate analyses and we will also examine whether latent variables of each construct provide an adequate fit and can be used in the analyses. The mediated effect will be obtained by multiplying coefficients for the regression of the mediators (either separate measures or latent constructs) on treatment condition and for the regression of drinks per drinking day at the 2-month follow-up on the mediators. We will use bootstrapping to obtain 95% confidence intervals of the mediated effect. We hypothesize the effects of active tDCS on drinks per drinking day will be mediated by greater mindfulness, greater inhibitory control and reductions in cue reactivity, craving, and negative affect in the active tDCS group, as compared to sham tDCS.

**EEG Analysis.** EEG analyses will focus on the association between EEG biomarkers (e.g., resting state alpha, theta, beta, and gamma activity, P3 amplitude during tasks) and drinking outcomes, as well as changes in behavioral task performance. Data will be analyzed using MATLAB-based signal processing toolboxes (e.g., EEGLAB, ERPLAB, EEGIFT). We hypothesize significantly increased P3 amplitudes during cognitive inhibition and reduced P3 amplitude in response to alcohol cues in the active tDCS group at post-treatment, as compared to sham tDCS.

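### In mediation models with post-treatment mediators, up to 14 of about 60 days of the 2-month drinking outcome can precede the mediator

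*Combined protocol and SAP*

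**What the plan says.** Two visits matter here, and both are timed from the end of treatment (Study Design, section V, Procedures & Interventions). The post-treatment visit takes place "up to two weeks after final tDCS/mindfulness session". For the follow-up visit the plan says: "At 2 months following completion of MBRP+tDCS, participants will complete the assessments listed in Table 1", without EEG. No tolerance is given around the 2-month date.

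The drinking outcome comes from the Form 90, a daily calendar interview: "A 2-month assessment window will be used at each of the time-points" (section V, Primary Drinking Outcome). The analysis section treats "drinks per drinking day at the end of treatment and follow-up as the primary outcomes".

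The mediation plan (Study Data, section II, Secondary Aim) reads: "Mediation models will be estimated for weekly and post-treatment assessments of mindfulness, inhibitory control, cue reactivity and craving, and negative affect". The mediated effect multiplies the effect of arm on the mediator by the coefficient from the "regression of drinks per drinking day at the 2-month follow-up on the mediators".

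Section V also lets the EEG session fall on a different day from the self-report, up to a week apart, and the behavioural tasks are run during EEG. Hypothesis 3 (Objectives/Aims) says of EEG: "Changes in ERPs among those who receive active tDCS with MBRP will be significantly associated with reductions in drinks per drinking day following treatment".

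The plan nowhere cuts the follow-up look-back at the post-treatment visit, and it does not mention that the two windows can share days.

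**The concern.** A mediation claim needs the mediator to be measured before the outcome it is said to influence. Here the 2-month outcome starts to accumulate at about the last session, while the post-treatment mediator may be measured up to two weeks later. Someone who drinks heavily in those two weeks may report more craving and more negative affect, or perform worse on control tasks, at the post-treatment visit. The same drinking is then scored in the 2-month outcome. Part of the fitted path from mediator to drinking would be a path from drinking to mediator.

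What is at stake is the reading of Hypothesis 2 for mediators taken at the post-treatment visit. It matters most for the behavioural tasks, which are not in the weekly battery and so have no correctly ordered during-treatment counterpart.

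**Working it through.** The documents give no figure for the overlap, so there is none to reproduce. It follows from the dates.

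**Inputs**
- Last session = day 0.
- Post-treatment visit at day d, with d from 0 to 14 (Post-Treatment Assessment).
- Follow-up visit 2 months after day 0 (Follow-Up Assessment).
- Form 90 look-back of 2 months at each visit (Primary Drinking Outcome).
- Assumption: 2 months = 60 days; range 56 to 62 shown below.

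**Windows**
- Follow-up outcome: day 60 − 60 = 0 to day 60.
- Post-treatment outcome: day d − 60 to day d.
- Outcome days before the mediator visit = d, a share of d/60 of the follow-up window. The same d days lie in both drinking windows.

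**Results**
- d = 0: 0 days, 0%.
- d = 7: 7/60 = 11.7%.
- d = 14: 14/60 = 23.3%.
- d = 14 with other lengths of 2 months: 14/56 = 25.0%, 14/61 = 23.0%, 14/62 = 22.6%.
- EEG and tasks a further 7 days later, if that week is added to the two weeks: 21/60 = 35.0%.

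**Sensitivity to the follow-up date.** If the follow-up visit is e days late, the window opens on day e and the overlap is max(0, d − e). With d = 14:
- 7 days late: 14 − 7 = 7 days, 11.7%.
- 14 days late: 0 days.
- 7 days early: 14 + 7 = 21 days, 35.0%.

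**Calendar days against data.** The outcome uses drinking days only, so the share of data can differ from the share of calendar days. With 2 drinking days in the first 14 and 23 afterwards, the share is 2/25 = 8%. With 14 and 10, it is 14/24 = 58%.

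**Which mediators.** The weekly battery (state mindfulness, practice, craving, urgency and planning items, negative affect) is completed at treatment sessions, on or before day 0. With the follow-up visit at 2 months, those measures precede the whole window. Only the post-treatment measures are out of order.

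**The case against.** The strongest objections concern what follows from the overlap, and several of them stand.

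**Hypothesis 1.** Because both time points are primary, a reader might infer that shared days bias the efficacy result. The documents do not support that. Randomisation protects the arm comparison at each visit, and the planned generalized linear mixed model allows outcomes within a person to be correlated, including through shared days. Nor does the plan present the two time points as separate periods or independent evidence. They share some days, and no more than that follows.

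**Hypothesis 3.** A reader might also infer that the ERP analysis requires the EEG change to come before drinking. The text states an association and does not tie it to the 2-month outcome. The point reaches ERPs only if the result is read as a mechanism for 2-month drinking, a reading made easy by its place under the mechanisms aim.

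**Weekly mediators.** For constructs also measured weekly, the plan already has a correctly ordered analysis. That limits the concern to post-treatment mediators.

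**Direction and size of bias.** The mediated effect is a product, so if arm affects neither the mediator nor drinking, overlap alone does not create mediation. This stands, but it is narrow. If active tDCS lowered drinking in the first two weeks by some other route, and drinking moved the mediator, both coefficients could be non-zero without the mediator doing anything. The documents give no correlations from which to size that bias, and none is claimed here.

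**Changing the primary outcome.** Starting the primary follow-up window at the post-treatment visit would replace a fixed window with one that depends on a post-randomisation attendance date, undefined for anyone who misses that visit. This objection holds, and the primary definition should stay.

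**Conclusion.** The point holds for one set of analyses: the regression of 2-month drinks per drinking day on post-treatment mediators. As the plan is written, up to 14 of about 60 calendar days (23%) of that outcome can precede the self-report mediator. For EEG and task measures the figure may reach about 21 days (35%) if the extra week is added to the two. These are maxima. They assume a follow-up visit at exactly 2 months, and the actual share varies between participants with the delay of the post-treatment visit, down to zero. The opening date of the window is derived from the two visit rules; the plan does not state it.

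The consequence is loss of temporal order in part of a secondary analysis. The efficacy comparison and the weekly-mediator analyses are not damaged. Because the correction is cheap, it is worth making.

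**What to change.** Leave the primary outcome definition unchanged. Add to the mediation section that, for models with post-treatment mediators and for any analysis relating post-treatment ERPs to 2-month drinking:

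- the outcome is drinks per drinking day from the day after the later of the post-treatment self-report and EEG/behavioural-task dates to the 2-month interview, computed from the daily Form 90 data;
- baseline drinking is adjusted for (the covariates named in the analysis section are gender, age and treatment history, plus variables associated with missing data);
- the same models on the full 2-month window are reported as a sensitivity analysis.

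The cost is a few sentences and a change of scoring syntax, with no new data. The window in these secondary analyses is up to 14 days shorter (60 − 14 = 46 days), or about 21 shorter if EEG falls a week later (60 − 21 = 39 days), and its length varies between participants. Anyone whose only drinking days fall before the start date has no drinking day left in the shorter window, so the scoring rule should cover that case. Participants without a post-treatment visit have no post-treatment mediator and no individual start date; they keep the full 2-month window. The change restores temporal order but does not remove confounding by a persistent drinking level, which can drive both the mediator and later drinking. The report should say so.
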